## 8.4 Screening and screening failures

### Subject identification number

Trial participation begins once written informed consent is obtained. Refer to Appendix 3B for details on the informed consent process. Once informed consent is obtained, a subject ID

will be assigned by a central interactive response technology (IRT) system, and the screening evaluations to assess eligibility criteria may begin. The subject ID will be used to identify the subject during the screening process and throughout trial participation, if applicable. Subjects who have given written informed consent to participate in the trial and who have been assigned a subject ID are considered 'screened' subjects.

The investigator will maintain a log of all consented subjects at the trial site (subject identification list). This log will include each subject's identity, date of consent, and corresponding subject ID so that any subject may be identified if required for any reason. The log must not be copied or retained by LEO. In addition, the investigator will maintain a log of all subjects considered for screening, whether they have provided written informed consent or not (screening log). This log will be anonymous and will include the reason(s) for not entering the trial, if applicable, or the allocated subject ID.

### Screening failures

Screening failures are defined as subjects who consent to participate in the trial but are not subsequently assigned to trial treatment. A minimal set of screening failure information is required to ensure transparent reporting of screening failure subjects to meet the Consolidated Standards of Reporting Trials (CONSORT) publishing requirements (25) and to respond to queries from regulatory authorities.

DLE is a rare disease, and the number of eligible patients is limited. Therefore, subjects who fail to meet all eligibility criteria at screening may be re-assessed for eligibility at a later stage at the investigator's discretion. This applies only to eligibility criteria that are likely to be fulfilled over time, e.g. criteria concerning DLE severity and prohibited medications.

Re-assessment of eligibility will be allowed at the investigator's discretion if one or more of the following eligibility criteria are not fulfilled at screening:

- Inclusion criteria no. 5, 6, and 7.
- Exclusion criteria no. 6, 7, 8, 9, 13, 14, 15, 16, and 19.

If any other eligibility criteria are not fulfilled at screening, the subject will be considered a screening failure. However, if the reason for screening failure is administrative (e.g. delayed test results and not due to the subject failing to fulfil the eligibility criteria), re-assessment of eligibility may also be permitted. Each subject can only be re-assessed for eligibility once.

At screening, it will be clearly documented in the eCRF and in the source data if a subject is planned to return for re-assessment of eligibility. Subjects who fail to return for re-assessment

of eligibility will be considered screening failures. Each subject will keep the same subject ID during the trial.

If the period between screening and re-assessment of eligibility exceeds 4 weeks, all screening procedures including laboratory samples must be repeated at the re-assessment visit. In this case, the re-assessment of eligibility will be documented as a full, additional screening visit in the eCRF. For shorter periods (<4 weeks) between screening and re-assessment of eligibility, the investigator will judge which assessments and procedures are relevant at the re-assessment visit.

The following data will be collected in the eCRF for screening failures:

- Date of informed consent.
- Demographics (date of birth, sex, ethnicity, race). If full date of birth is not allowed to be recorded per local legislation, month and/or year of birth should be collected together with the subject's age.
- Reason for screening failure.
  - Failure to meet eligibility criteria.
  - Lost to follow-up.
  - Withdrawal by subject.
  - Other.
- Date of screening failure.
- Any adverse events (AEs) and serious AEs (SAEs).

In case of any SAEs, these must be followed up as described in Section 13.7.

## 9 Treatments

### 9.1 Trial product description

Delgocitinib is a pan-JAK inhibitor, which is presented in this trial as a cream formulation for topical application. Please refer to Panel 4 for further details.

**Panel 4: Identification of investigational medicinal products**

| Investigational medicinal product | Dosage form | Active ingredient and concentration | Pack size | Source         |
|-----------------------------------|-------------|-------------------------------------|-----------|----------------|
| Delgocitinib cream 20 mg/g.       | Cream.      | Delgocitinib 20 mg/g.               | 15 g.     | CCI [REDACTED] |
| Delgocitinib cream vehicle.       | Cream.      | Vehicle.                            | 15 g.     | CCI [REDACTED] |

**9.2 Administration of IMP**

The IMPs (delgocitinib cream and vehicle) will be administered as topical applications twice daily for 6 weeks. The 2 target lesions (referred to as lesion 1 and 2, see Section 11.2.8) will be randomised 1:1 to treatment with delgocitinib cream 20 mg/g or vehicle. The subjects will apply the IMPs in the morning and in the evening, approximately 12 hours apart. Instructions for use will be provided.

For each target lesion, the treatment area will be defined as the lesion area at baseline plus a margin of approximately 1 cm. The first application of the IMPs will occur on Day 1 at the trial site after all assessments have been completed. Prior to the first IMP application, the subjects will be instructed how much cream to apply and which IMP to use on each treatment area. The instructions will be given by trial site staff who are not involved in clinical assessments during the trial. The identification of the 2 target lesions and the allocation of treatment to each lesion is further described in Section 9.3.

The amount of IMP to be applied to each treatment area depends on the size of the target lesions. If a target lesion remains unchanged or decrease in size, the treatment area will remain constant during the treatment period even if the symptoms improve. If a target lesion increases in size, the treatment area will increase correspondingly. The IMPs should be applied in an even layer to cover the entire treatment area. The maximum expected treatment area is 1% of BSA corresponding to a lesion of 15 cm in diameter. For reference, it is estimated that 0.3 g of cream will be adequate to cover 1% of BSA (an area corresponding to the subject's hand; the palmar surface plus the 5 digits).

The subjects will continue treatment until visit 5 (Week 6) regardless of clearance status. The last application of the IMPs will occur at the subject's home the day before the subject attends the Week 6 visit.

The subjects should not shower within 2 hours after applying the IMPs. At the scheduled visits, investigator assessments and PaGA should be done prior to or at least 2 hours after IMP application and/or bathing/showering. Non-invasive skin sampling should be done prior to or at least 4 hours after IMP application. Note that on the day of the Week 6 visit, no IMP will be applied in the morning.

In addition to the IMPs, all subjects should apply sunscreen every day during the treatment period (Section 9.4). The sunscreen should be applied to sun-exposed areas in the morning, at least 45 minutes after application of IMP.

On the treatment areas, only the IMPs and sunscreen can be applied. On DLE lesions outside the treatment areas, only sunscreen and emollients are allowed (see also Section 9.7). This is to avoid confusing the subjects by having to apply more than 2 treatments, as accidental use of other medications on the treatment areas could impact both efficacy and safety assessments.

The IMPs will be dispensed at the visits shown in the schedule of trial procedures (Section 4).

LEO does not recommend specific treatment for an overdose. The investigator will use clinical judgement to treat any overdose if necessary (Section 13.6.2).

### **9.3 Treatment assignment**

Subjects who have been found to comply with all the inclusion criteria and not to violate any of the exclusion criteria will be assigned to treatment at baseline (Day 1).

All subjects will receive the same 2 treatments (delgocitinib cream and vehicle), so there will be no subdivision into treatment groups. At screening, 2 potential target lesions are selected and evaluated. At baseline, the potential target lesions are re-evaluated. In the unlikely event that 1 or both of the potential target lesions selected at screening no longer fulfil all the eligibility criteria at baseline, the investigator is allowed to select new, eligible target lesions (if available) at baseline, as long as this is clearly documented in the source data and the eCRF (see Section 11.2.8).

After confirmation of eligibility at baseline, the selected target lesions will be numbered as lesion 1 and 2. The numbering should begin with the uppermost or most proximal site on the left from the investigator's view. Lesions along the same line should be numbered from left to right.

Randomisation will be performed by permutation of the treatment codes A and B. Each subject will be randomly assigned to either the treatment sequence AB or the treatment sequence BA with the probability 0.5. The first treatment listed in the treatment sequence will be assigned to lesion 1 and the last treatment will be assigned to lesion 2.

The IRT system will assign the required kit number for each subject and will also be used for IMP supply chain and expiry tracking.

### **9.3.1 Blinding**

The packaging and labelling of the IMPs will contain no evidence of their identity. However, there is a slight difference in colour between the 2 IMPs. The difference is only discernible on close inspection with both IMPs compared side by side. To avoid accidental investigator unblinding, the first application of IMPs and instructions to the subjects will only be done by designated trial site staff who are not involved in clinical evaluations.

### **9.3.2 Emergency unblinding of individual subject treatment**

While the safety of a subject always comes first, it is still important to carefully consider if unblinding is necessary to ensure a subject's safety. In many cases, IMP discontinuation and knowledge of the possible treatment assignment are sufficient to treat a trial subject who presents with an emergency condition. An emergency unblinding request can be made by the investigators, health care professionals who are not members of the trial staff, or authorised LEO personnel.

Provisions are in place for 24-hour emergency unblinding of individual subject treatment. If emergency unblinding is required, the investigator can unblind a subject's treatment in the IRT system. For a requester who is not a member of the trial staff and who does not have access to the IRT system (e.g. a physician at an emergency room), a local contact number for the emergency unblinding CRO is provided on the subject card (see Appendix 3B) to be used if the investigator or delegated site staff cannot be reached. The requester will provide the trial ID and subject ID to the emergency unblinding CRO who will immediately reveal the individual treatment allocation.

The emergency unblinding CRO will clarify that the requester requires immediate unblinding without further medical consultation. Should the requester wish to discuss whether unblinding is necessary, the emergency unblinding CRO will provide the requester with the LEO 24/7 contact which will be diverted to the medical cover.

#### **9.4 Background treatment**

All subjects will be instructed to apply sunscreen daily to sun-exposed areas during the treatment period. The sunscreen must have a sun protection factor (SPF) of at least 50 and will be provided to all subjects by the trial site. If the subject is known to be hypersensitive to the provided sunscreen or has a strong preference for a particular brand, the subject can be allowed to use his/her preferred sunscreen with SPF of at least 50. The sunscreen should be applied in the morning, at least 45 minutes after application of IMP.

#### **9.5 Rescue treatment**

Not applicable.

#### **9.6 Concomitant medication and concurrent procedures**

Current medication or vaccines from baseline through safety follow-up as well as medication listed as prohibited medication in the exclusion criteria that the subject receives from 6 months prior to baseline must be recorded (if relevant) in the subject's medical record and the eCRF along with details such as:

- Medication name.
- Indication.
- Start and stop date of administration (it will also be recorded if the medication is ongoing).
- Dosage information, including dose, unit, and frequency.
- Route of administration.
- For topical treatment, the body location must be recorded. It must also be recorded if the treatment is within 5 cm of a target lesion (and if so, which of the target lesions).

Any concurrent procedure from baseline through safety follow-up as well as procedures listed as prohibited procedures in the exclusion criteria from 4 weeks prior to baseline must also be recorded in the subject's medical record and the eCRF. The following details will be recorded:

- Procedure.
- Body location.
- Diagnosis.

- Start and stop date (it will also be recorded if the procedure is ongoing).
- For cutaneous procedures, it must also be recorded if the procedure is inside a target lesion (and if so, which of the target lesions).

Investigators may prescribe concomitant medications or treatments to provide adequate supportive care as deemed necessary, except for medications listed in Section 9.7. The sponsor's medical expert should be contacted if there are any questions regarding concomitant or prior therapy.

If analgesic treatment is considered necessary during the trial, the following concomitant medications are recommended and allowed from screening through safety follow-up:

- For subjects with mild SLE: ibuprofen  $\leq 1200$  mg/day (or equivalents in their corresponding recommended maximum daily dose), provided that this is known to be well tolerated by the subject.
- For subjects without SLE: paracetamol  $\leq 4000$  mg/day should be used instead of ibuprofen.

## 9.7 Prohibited medication and procedures

The medications listed in Panel 5 are prohibited during the trial. Note that some medications are prohibited prior to screening and/or randomisation, but allowed during the treatment phase (see the exclusion criteria, Section 8.3). Note that any changes in dose or discontinuation of medications or procedures that are listed as prohibited prior to or during the trial should only be done for medical reasons, not trial-related reasons.

**Panel 5: Prohibited medication and procedures**

| Medication/procedure  | Prohibited from  | Prohibited to |
|---|--|---------------|
| Systemic prednisolone >7.5 mg/day or changed dose (nasal and inhaled corticosteroids allowed).  | 4 weeks prior to baseline.   | End of trial. |
| Oral antimalarial treatment with hydroxychloroquine >6.5 mg/kg/day or chloroquine >4 mg/kg/day, or changed dose.                                  | 12 weeks prior to baseline.  | End of trial. |
| Quinacrine combined with either hydroxychloroquine or chloroquine.  | 12 weeks prior to baseline.  | End of trial. |
| Drugs known to interact with antimalarials (e.g. digoxin, cimetidine) a .  | 12 weeks prior to baseline.  | End of trial. |
| Immunosuppressive/immunomodulating therapy with e.g. methotrexate, cyclosporine, azathioprine, retinoids (both topical and systemic), or dapsone. | 4 weeks prior to baseline.   | End of trial. |
| Biologics (cell-depleting agents including but not limited to rituximab).   | 6 months prior to baseline or until lymphocyte count returns to normal, whichever is longer. | End of trial. |
| Other biologics.  | 3 months or 5 half-lives prior to baseline, whichever is longer.                             | End of trial. |
| Topical corticosteroids, calcineurin inhibitors, and PDE-4 inhibitors.  | 2 weeks prior to baseline.   | End of trial. |
| Any cutaneously applied product (other than sunscreen and IMPs) on the treatment areas.   | Randomisation.   | End of trial. |
| Any cutaneously applied product (other than sunscreen and emollients) on DLE lesions outside the treatment areas.                                 | Randomisation.   | End of trial. |
| Cutaneously applied antibiotics on the treatment areas.   | 2 weeks prior to baseline.   | End of trial. |
| UV therapy or excessive sun exposure.   | 2 weeks prior to baseline.   | End of trial. |
| Live (attenuated) vaccine.  | 4 weeks prior to baseline.   | End of trial. |
| Any non-marketed drug substance (i.e. an agent which has not yet been made available for clinical use following registration).                    | 4 weeks or 5 half-lives prior to baseline, whichever is longer.                              | End of trial. |
| Any procedure impairing the skin barrier (e.g. incision) within 2 cm from the border of any of the target lesions.                                | 4 weeks prior to baseline.   | End of trial. |

a) Only applicable to subjects taking antimalarial treatment.

**Abbreviations:** DLE = discoid lupus erythematosus; IMP = investigational medicinal product; PDE-4 = phosphodiesterase; UV = ultraviolet.

In case any prohibited treatments are used during the trial, they must be recorded as concomitant medication.

Normal bathing and washing is allowed following the subject's normal routine but should be done at least 2 hours after application of the IMPs.

Use of cosmetic body care products (e.g. make-up, body lotion, bath oil) and emollients is not allowed on the target lesions from baseline to safety follow-up.

## **9.8 Treatment logistics and accountability**

### **9.8.1 Labelling and packaging of trial products**

#### **Investigational medicinal products**

The IMPs will be packaged in individually numbered kits. Primary and secondary packaging materials will be individually labelled. The 2 IMPs (treatment A and B) will have labels in different colours to help the subjects distinguish between them.

The labelling of IMPs will be in accordance with Annex 13, local regulations, and trial requirements. Label text will be translated into local languages, as required.

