#### **9.8.4 Treatment compliance**

The first application of IMPs will occur at the trial site with clear instructions from the site staff on which IMP to use on each target lesion and how much IMP to use per application (see Section 9.2).

At the visits specified in the schedule of trial procedures (Section 4), the subject will be asked if they have used the IMPs as prescribed. If a subject is found to be non-compliant, the investigator should remind the subject of the importance of following the instructions given, including applying the IMPs as prescribed. It must be recorded in the eCRF whether the subject is compliant or non-compliant. For non-compliant subjects, the reason for non-compliance and the nature of non-compliance (i.e. the number of missed or excessive applications of IMP, or use of the wrong IMP on 1 or both target lesions) will also be recorded.

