#### Panel 6: Sequence of assessments

- a) At the screening visit, the subject's eligibility to enter the trial must be confirmed before any subject assessments can be completed.
- b) Photographs of lesions (optional), non-invasive skin sampling, skin biopsies (optional).

Subjects participating in the trial will be under careful supervision of a principal investigator who must be a dermatologist. Investigators must be physicians who are experienced in treating DLE and have documented experience and/or training in use of the assessments

required by the protocol. In United States, the investigator can also be a certified physician's assistant or advanced registered nurse practitioner.

AEs must be assessed by medically qualified personnel (Section 13.2).

Whenever possible, the same investigator should perform all the evaluations for a given subject throughout the entire trial period to reduce inter-rater variability.

The investigator(s) performing the assessments must not be involved in the administration of IMPs (see Section 9.3.1).

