**Risk assessment**

In this trial, the risks to critical trial processes and data have been evaluated. The main risk is recruitment problems, as DLE is a rare disease. This risk will be addressed by thorough feasibility analysis during the trial planning phase.

Other identified risks are:

- Inconsistency within the primary endpoint data due to IGA inter-rater variability.
- Accidental investigator unblinding due to slight differences in colour between the 2 IMPs.
- Accidental use of the wrong IMP on 1 or both target lesions.

Risk mitigation activities to ensure data quality and subject safety include:

- To ensure consistent efficacy assessments (IGA), all assessors will receive training before starting the trial. Whenever possible, the efficacy assessments will be made by the same investigator at each visit for a given subject to reduce inter-rater variability.
- To avoid unblinding, sites will be required to assign a staff member who is not involved in clinical assessments to apply the first IMP doses at the baseline visit.

- To ensure that the subjects apply the IMPs to the correct lesions throughout the trial, the subjects will receive a body diagram illustrating the location and assigned treatment of each target lesion at the baseline visit as a reference/reminder.

In addition, to ensure consistent AE monitoring and avoid duplicate AE reports, CRO staff conducting the exit interviews will be properly trained to detect and report any AEs that might be reported during these interviews (Section 13.2).

Throughout the trial, regular data quality review meetings will be held to ensure continuous improvement of data quality and prevention of mistakes. During monitoring visits at the trial sites, the CRAs will verify that investigators work according to the protocol.

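### Does colouring the tube labels by treatment code mean that one emergency code break unblinds other subjects?

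*Combined protocol and SAP*

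**What the plan says.** On labels, Section 9.8.1 says: "The 2 IMPs (treatment A and B) will have labels in different colours to help the subjects distinguish between them". On allocation, Section 9.3 says: "Each subject will be randomly assigned to either the treatment sequence AB or the treatment sequence BA with the probability 0.5". The first code in the sequence goes to lesion 1 and the second to lesion 2, so every subject receives both products and handles both colours.

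On code breaks, Section 9.3.2 says: "If emergency unblinding is required, the investigator can unblind a subject's treatment in the IRT system". The provision concerns the individual subject. The section does not say what the system displays, and it sets no rule on whether someone who has broken one code may go on assessing other subjects.

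On separating raters from product, Section 9.3.1 says that "the first application of IMPs and instructions to the subjects will only be done by designated trial site staff", namely staff with no part in clinical evaluations. Section 11.1 adds: "The investigator(s) performing the assessments must not be involved in the administration of IMPs".

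On compliance, Section 9.8.4 says of a non-compliant subject that "the investigator should remind the subject of the importance of following the instructions given, including applying the IMPs as prescribed". The nature of the non-compliance is recorded, including "use of the wrong IMP on 1 or both target lesions". To help subjects keep the tubes apart, Appendix 3D (Risk assessment) says that "the subjects will receive a body diagram illustrating the location and assigned treatment of each target lesion at the baseline visit".

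**The concern.** AB/BA randomisation makes most sense if A is one product and B the other for the whole trial. Colour would then equal product for every subject. A person who breaks one code and knows that subject's tube colours holds the colour key for up to 44 others. With the key and another subject's colour-to-lesion link, that person can name the active lesion with certainty. If colour followed lesion number, label colour would give only a 50% guess.

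The contrast is within subject and the IGA is a judgement. A rater who knows the active lesion could score it down and the vehicle lesion up, and both shifts would enter the treatment difference. Section 9.8.4 looks like a way for the colour-to-lesion link to reach a rater: it gives the investigator the follow-up of non-compliance and does not say that a non-assessor does it. Appendix 3D lists accidental investigator unblinding as a risk, but only through the slight colour difference between the creams.

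**Working it through.** **The plan's own figures.** Section 14.1 gives 36 completers, 20% drop-out, and clearance of 5% (vehicle) and 35% (delgocitinib).

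- Randomised: 36 / (1 − 0.20) = 45, as stated.
- Power with independent lesions: discordant probability = 0.35 × 0.95 + 0.05 × 0.65 = 0.365; SD = √(0.365 − 0.30²) = 0.524; Φ(0.30 × √36 / 0.524 − 1.96) = 0.930, in line with the stated 90%.

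Labelling changes none of these. The question is how far a leak would raise false rejection.

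**What must happen before a second subject is unblinded.**

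1. Colour is fixed to product across the trial (inferred, not stated).
2. A code is broken. Every subject is known to receive active drug on one lesion, so a break adds only which lesion. Section 9.3.2 notes that stopping the IMP and knowing the possible assignment are often enough. No break rate is given. Assuming 0.5%, 1%, 2% or 5% per subject, 1 − (1 − q)^45 gives a 20%, 36%, 60% or 90% chance of at least one break. The sizes below therefore assume that a break has happened.
3. The person who breaks the code also learns that subject's tube colours.
4. That person rates another subject still on treatment and learns that subject's colour-to-lesion link.

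**Reach.** With about 20 sites (Section 7.2), 45 / 20 = 2.25 subjects per site, so 1.25 others. As a share of the trial, 1.25 / 45 = 2.8%.

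**Effect on the primary test.** Assumptions: no true effect, n = 36, independent lesions, 10% success on both, and every affected subject shifted by +10 points on active and −10 on vehicle.

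- Shift averaged over the trial: 0.0278 × 10 = 0.28 points, giving 10.28% against 9.72%.
- Active-only success: 0.1028 × (1 − 0.0972) = 0.0928.
- Vehicle-only success: 0.0972 × (1 − 0.1028) = 0.0872.
- The number of discordant pairs m is binomial (36, sum of these two). Summing over all outcomes, the uncorrected test rejects when (difference)² / m > 3.84, and the exact test when 2 × P(Bin(m, 0.5) ≤ smaller count) ≤ 0.05.

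| Subjects affected | Active vs vehicle | Uncorrected | Exact |
|---|---|---|---|
| None | 10% vs 10% | 4.70% | 1.44% |
| Rest of one average site (2.8%) | 10.28% vs 9.72% | 4.76% | 1.47% |
| One whole site (5%) | 10.5% vs 9.5% | 4.9% | 1.5% |
| Five sites (25%) | 12.5% vs 7.5% | 9.7% | 4.0% |
| 30% of subjects | 13% vs 7% | 12.1% | 5.4% |
| Ten sites (50%) | 15% vs 5% | 27% | 15% |

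At the protocol's 5% vehicle rate the downward shift cannot exceed 5 points. One whole site then moves rejection from 3.7% to 4.0% (uncorrected) or from 0.3% to 0.4% (exact).

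The second row is the case that one code break at an average site could produce. The spurious difference there is 10.28 − 9.72 = 0.56 points, against a planned difference of 30. The lower rows need the key to travel between sites, and nothing in the protocol describes how it would. Even the second row is generous: it counts subjects who may already have finished and assumes each is fully unblinded.

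**The compliance route.** Subjects known to have used the wrong IMP on either lesion leave the per-protocol set (Section 14.2), which is primary for the primary endpoint (Section 14.3.4). The conversation most likely to reveal a colour-to-lesion link therefore concerns subjects outside the main analysis, although they stay in the full-analysis-set sensitivity analysis. Talk of missed or extra applications need not reveal colours.

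**The case for a change.** The strongest case for acting is that the leak is real on the natural reading and the text does not close it. Section 9.8.4 leaves open who does the compliance check. Labelled tubes return to the site at Weeks 2, 4 and 6, and the subject holds a diagram of treatment by lesion and rates the PaGA. Colour by lesion would remove the label cue altogether. Some remedies need only a sentence: name a non-assessor for the compliance check, or log each code break and who learned of it.

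The mechanism stands, and so does the silence on who does the check. The case for changing the plan does not follow. Sections 9.2, 9.3.1 and 11.1 and Appendix 3D already keep assessors away from application and instructions, and a site that follows them will naturally give product conversations to the same designated staff. Writing that down would record sensible practice without altering a result. The PaGA endpoints are exploratory.

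Colour by lesion is not a cheap correction. Each product would need both label colours, so four tube and label combinations at packing. Both sequence types would have to be stocked at about 20 sites averaging 2.25 subjects, whereas the present A and B tubes serve either sequence. A lost tube might mean replacing the pair. At version 4.0, packed stock would need relabelling or a changeover, which could itself cause mix-ups, and wrong-IMP use is already a listed risk. The cream colour difference would remain.

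**Conclusion.** No change follows. If label colour is fixed to product, a code break for one subject could in principle give the colour key for others, but several unlikely steps must coincide and the assessor separation works against the last of them. Once a break has happened at an average site, the effect on false rejection is about 0.06 percentage points (4.70% to 4.76%) with the uncorrected test and 0.03 (1.44% to 1.47%) with the exact test. This rests on an assumed 10% success rate, an assumed 10-point shift each way, independent lesions, and full unblinding of 1.25 other subjects. At 10% success the exact test passes 5% only when about 30% of subjects are affected, and the protocol shows no route to that. The trial is an exploratory phase 2a study whose tests are read descriptively (Section 14.3.11). Colour by code is a fair trade-off between simple supply and a very small residual risk. Colour by lesion is an option for a later trial's packaging.
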